### **c. Study Design**

This study will take place in Chicago, Illinois at three sites with many years of supporting HIV prevention research: Chicago House and Social Service Agency (Chicago House), Ann & Robert H. Lurie Children’s Hospital of Chicago (Lurie Children’s) and University of Chicago (U of C). Study visits will take place at Chicago House and Lurie Children’s or, due to the COVID-19 pandemic, may occur virtually via teleconference or telephone; intervention delivery will occur at Chicago House or virtually via teleconference or telephone. Primary data analysis of de-identified data will take place at U of C and Lurie Children’s.

The specific aims of the study are as follows:

1. To determine the pre-post efficacy of the TLC intervention in a single arm trial on the primary outcome: number of condomless anal sex acts without protection by PrEP in the last month among 150 sexually active, HIV-uninfected TW (ages 17 and older), with assessments at baseline, 4 and 8 months.
  - a. To assess the dose response relationship by intervention exposure (i.e., the proportion of intervention components received/expressed need) as well as exposure to specific components (i.e., employment, housing, legal, and health) on reductions in the primary outcome.
  - b. To assess mediation of intervention effects on protective processes (gender affirmation, collective self-esteem, social support) theorized to increase with intervention exposure;
2. To examine the implementation experiences of TLC intervention participants and staff through semi-structured interviews with 20 TLC participants and 10 TLC and Chicago House staff members involved in delivery of services through the TLC intervention.
3. Exploratory Aims:

- a. To describe the trajectory of PrEP indication, uptake, retention and adherence in the community-based sample over an 8-month follow-up period and evaluate the impact of the TLC intervention on the PrEP continuum of care.
- b. To explore whether reductions in HIV risk are associated with epidemiologically-linked moderators including age and race/ethnicity.

Primary Hypotheses: We hypothesize that participants in the TLC intervention will demonstrate a reduction in number of condomless anal sex acts not protected by PrEP pre-post intervention.

Primary Outcome: The primary outcome of interest is the number of condomless anal sex acts without protection by pre-exposure prophylaxis (PrEP) reported in the previous month.

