### **i. Variables**

*Primary outcome:* The primary outcome, condomless anal sex acts not protected by PrEP adherence (defined as anal sex acts without a condom in the prior month without use of PrEP at protective levels) will be analyzed as a composite variable of condomless anal sex acts that confer risk in the prior month, adjusting condomless acts to “0” for those participants with protective levels of PrEP adherence verified by biomarker (i.e., hair analysis, see below). We will use the AIDS-Risk Behavior Assessment (ARBA; revised for transgender women) for measurement of sexual risk. The ARBA is a computerized self-interview designed to assess self-reported sexual behaviors. Self-reported PrEP adherence will be measured using time-line follow-back (TLFB) for the 1-month recall period. Objective verification via hair samples will only be completed for those individuals who report levels of adherence consistent with protection over the entire recall period (i.e., 4 doses/week for PrEP). We will collect hair samples (100 strands) for analysis of uptake/adherence to PrEP (tenofovir disoproxil fumarate). Hair analysis will be completed at the University of California (UCSF) Hair Analysis Lab. Among participants from whom a hair sample is not feasible, either due to short hair or hair extensions, for example, a blood sample will be collected via a dry blood spot (DBS), for analysis of PrEP level. The DBS will be collected by venipuncture (4mL of blood or approximately one teaspoon). DBS processing and analysis will be performed by University of Colorado. During the COVID-19 pandemic, no hair or DBS samples will be collected at any time point.

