Analyses will be conducted with SAS software (SAS Institute, Cary, NC). To determine the pre-post efficacy of the TLC intervention, we will assess the change in number of condomless anal sex acts from baseline to 4 and 8 months using paired t-tests or Wilcoxon signed rank tests for continuous outcomes, and McNemar's test for paired proportions for categorical outcomes. To maximize power, extensions of generalized linear models (GLMs) will be used to assess the combined effect of the intervention on condomless anal sex at 4 and 8-month follow-up. GLMs can accommodate dependent variables with normal, binary, Poisson, and negative binomial distributions and can be adapted to incorporate random and fixed effects (generalized linear mixed models; GLMMs) to account for within-subject correlation among repeated measures over time. Multivariable GLMMs will be used to assess frequency of condomless anal sex not protected by PrEP at 4- and 8-months post baseline, with an indicator for time as the primary explanatory variable. Models will also include the baseline value of the outcome, and covariates (e.g., age, race) that will be selected based on a priori hypotheses and empirical or theoretical importance. In the original analytic plan we proposed to treat time as discrete, assuming all visits occurred at 4 and 8 months within a margin of error. To account for differences in time between baseline and follow-up visits due to COVID-19 related changes in the recruitment protocol (i.e., extension of 4 and/or 8 month windows), we will conduct additional supplemental analyses to account for variability in person-time contribution among participants. We will calculate the exact time in days between baseline and subsequent visits as a continuous variable, and pre-post analyses will control for the time between measurements. For evaluation of the effect of intervention dose on rates of condomless anal sex over time, we will estimate relative rate ratios by specifying log-time as an offset variable in generalized linear models to account for varying person-time contributions. We will also include an indicator for whether stay at home orders were in place at the time of the assessment to control for behavioral changes that may have resulted from COVID-19 related policies. The analytic approach and interpretation of intervention effect estimates will otherwise be analogous to those described in the original proposal. Potential confounding and effect modification by sociodemographic characteristics and other factors will be examined in exploratory analysis and will be included in multivariable models as appropriate. All models will account for correlation among repeated measures on individuals over time. Inclusion of random effects for intercept and trend over time will be explored to assess subject-specific variability at baseline and in terms of trajectories over time.

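### The stay-at-home indicator is dated to the visit, but the primary outcome counts acts in the month before it

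*Protocol*

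**What the plan says.** Protocol II.c (Study Design) defines the primary outcome as "the number of condomless anal sex acts without protection by pre-exposure prophylaxis (PrEP) reported in the previous month". Protocol III.c.i (Variables) repeats the period: "anal sex acts without a condom in the prior month without use of PrEP at protective levels".

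Protocol III.d (Data Handling and Analysis) makes two adjustments for the pandemic.

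- **Stay-at-home orders.** Models include "an indicator for whether stay at home orders were in place at the time of the assessment", and the stated purpose is "to control for behavioral changes that may have resulted from COVID-19 related policies".
- **Visit timing.** Because visit windows were extended, the Protocol says "we will conduct additional supplemental analyses to account for variability in person-time contribution among participants". The covariate is defined in these words: "We will calculate the exact time in days between baseline and subsequent visits as a continuous variable". Its use is given as follows: "pre-post analyses will control for the time between measurements". The Protocol does not say whether days are centred, or at what time the adjusted pre-post effect is read. It does say that interpretation of the effect estimates otherwise stays as planned before the pandemic.

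**The concern.** Behaviour is measured over a month, but the exposure meant to explain it is measured on one day at the end of that month. Around the start and end of every order the two disagree. A visit a few days into an order is coded exposed although most of the recalled acts fell before it. A visit a few days after lifting is coded unexposed although most of the recalled month was under the order.

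This matters because the trial has one arm. Without a concurrent control, a pandemic-related change in sexual contact between baseline and follow-up can pass for an intervention effect, or hide one. The indicator is the only covariate that III.d names for this purpose. A confounder measured with error is only partly adjusted for.

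The days variable raises a lesser question. If raw days stand beside a baseline-to-follow-up term, that term no longer means the change at 4 or 8 months.

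**Working it through.** The Protocol gives no figure on this point, so there is none to reproduce. It gives no order dates or lengths either, so order length L is an assumption.

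**Indicator.** Inputs: recall of one month (II.c, III.c.i), taken as 30 days; indicator read on the visit day (III.d); one order of L days, L at least 30; visits spread evenly over the L + 30 days on which the recalled month can touch the order.

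- A visit u days into the order (u below 30) has true share u/30 and is coded 1. The error is 1 − u/30, which sums to 15 over the 30 days.
- A visit v days after the end (v below 30) has true share (30 − v)/30 and is coded 0. The error is (30 − v)/30, which again sums to 15.
- All other visits are coded correctly.
- Miscoded share = 60/(L + 30). Mean absolute error over all touching visits = 30/(L + 30).

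| Assumed L (days) | L + 30 | Miscoded share | Mean error (share of month) |
|---|---|---|---|
| 60 | 90 | 67% | 0.33 |
| 75 | 105 | 57% | 0.29 |
| 90 | 120 | 50% | 0.25 |

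A day-by-day count agrees. In the 30 days after an order ends, all visits are coded 0, while on average 52% of the recalled month was under the order (at least half for 16 of the 30 days). In the first 15 days of an order, visits are coded 1 with less than half the month exposed. Among visits coded 1, the mean exposed share is 74% for a 60-day order and 83% for a 90-day order.

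**Days since baseline (illustrative, and only if entered raw).** Inputs: 120 evaluable participants (III.b.ii, Sampling). Assumptions: true mean change −0.30 SD of the change; visits near day 240 with SD 10 days; either no further delay, or 40% delayed by up to 60 or 180 days.

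Regress the change on days. With raw days the intercept is the change at day 0, and its SE is (1/√n) × √(1 + mean²/variance of days). With no delay this is 0.091 × √(1 + (240/10)²) = 2.19. Simulation gives 2.23, against 0.09 with days centred at their mean. With delays of up to 180 days, the mean is 240 + 0.4 × 90 = 276 and the variance is 0.4 × 180²/3 − 36² + 100 = 3,124 (SD 55.9). The SE is then 0.091 × √(1 + (276/55.9)²) = 0.46; simulation gives 0.47.

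- Effect growing in proportion to time: the raw-days estimate is about 0 (−0.08 to 0.01), with rejection in 5% to 7% of runs.
- Step effect: the estimate stays at about −0.29 to −0.30, but power falls from about 90% to 5–10%.
- Three-visit model with a post-baseline indicator plus raw days, 40% delayed by up to 120 days: a growing effect goes from −0.34 to 0.01. A step effect stays at −0.30, with power down from 97% to 45%.
- With days centred among follow-up visits, estimate and power match the unadjusted model.

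**The case against.** **The indicator's error is confined to the edges of orders.** This stands. The 50% to 67% applies only to visits whose recalled month touches an order, and counts any discrepancy, however small. As an illustration, assume one order and visits spread evenly over 18 months of enrolment plus 8 of follow-up (26 × 30.4 = about 790 days). Then 60/790, about 8% of all visits, are miscoded, by half a month on average. More orders, or visits bunched near their edges, would change this. A reader might infer that most visits in the trial are misclassified; the documents do not support that.

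**No bias in the effect estimate is shown.** This also stands. Size and direction depend on when orders fell relative to baseline and follow-up visits, which the documents do not give. The sentence also sits within the COVID-19 additions, so it is not certain that the indicator belongs to the primary model.

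**The indicator is not the only safeguard.** III.d also plans to examine confounding by sociodemographic and other factors, so calling it the sole protection would be too strong. Neither those factors nor days since baseline measure exposure to orders.

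**The days adjustment may be harmless.** A reader might infer that it absorbs the intervention effect. The text does not support that. It never says days are uncentred, it labels these analyses supplemental, and a statistical analysis plan may fix the coding. The mixed models are described for 4- and 8-month outcomes with the baseline value as a covariate; on that reading there is no baseline-to-follow-up term for days to duplicate. The unadjusted paired tests are untouched. What survives is a conditional caution.

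**Conclusion.** The mismatch between the indicator and the recall period stands on the Protocol's own wording, and an analysis that follows the sentence inherits it. For an assumed order of 60 to 90 days and a 30-day recall, 50% to 67% of visits whose recalled month touches the order carry a wrong exposure value, by 25% to 33% of the month on average over all such visits. Visits well inside or outside an order are unaffected. The consequence is weaker control of pandemic-related behaviour change in a design without a control arm, not a demonstrated bias.

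The days point is secondary. If raw days are entered beside a pre-post term, that term becomes an extrapolation to day 0. It is then biased towards no effect if the effect grows with time, and unbiased but imprecise if the effect is a step. Gradual growth is plausible, since III.c.ii has services delivered throughout the 8 months, but the Protocol does not commit to raw entry.

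**What to change.** Replace the indicator with the fraction (0 to 1) of the one-month recall window that fell under stay-at-home orders. Compute it at every visit, including baseline, because the pre-post contrast depends on exposure at both ends.

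In the supplemental time-adjusted pre-post analyses, enter days as actual minus planned visit day (0 at baseline), and state that the effect is read at the planned 4- and 8-month times.

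The cost is a change of wording and two derived variables, with no new participant data. The Protocol already plans to compute exact days from visit dates. It does not say that order dates are held, but the planned indicator needs them too, so a short list of start and end dates suffices. Reading the effect at the planned day rather than the mean observed day costs a little precision when delays are long. In the 180-day illustration the SE is 0.091 × √(1 + (36/55.9)²) = 0.109 instead of 0.091, far below the 0.46 with raw days.

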
#### **e. Handling of Adverse Events**

Possible adverse events (AEs) that are anticipated in this study include the need to violate the confidentiality of the participants in the case of spontaneously reported suicidality. All study personnel will be trained regarding the limits of confidentiality. The training will include reviewing possible scenarios and knowledge of key questions to assess risk. We will train staff to err on the side of caution

and to contact the clinical supervisor as needed. Supervisors and Investigators will be available on site or via phone after hours should staff need consult regarding an emergency. In this situation, we will train all staff to immediately contact clinical supervisors before participants leave the interview room. Under the guidance and direction of clinical supervisors, study staff will be trained when to either contact police to ensure the safety of participants, or if appropriate, to escort participants to the nearest Emergency Room, which is located close (less than 1 mile) to the primary recruitment sites.

Possible adverse events (AEs) that are unanticipated will be brought to the attention of the study PIs and reported immediately to the IRB and to the CDC. The study PIs will report the AEs and serious AEs (SAEs) to the IRB in writing as soon as possible, but within 7 calendar days for death or life-threatening events and within 15 calendar days for all other AEs or SAEs. The IRB will determine whether it is appropriate to stop the study protocol temporarily or will provide suggestions/modifications to the study procedures as necessary. Possible modifications include adding these possible adverse events to the consent form and re-consenting all study participants. The PIs will be responsible for monitoring participant safety on a monthly basis at regularly scheduled research meetings. They will keep a written log of all events and ensure that the IRB and the CDC are contacted immediately. They will also keep a log of the outcome of IRB decisions regarding adverse events and apprise the research team of any changes that need to occur as a result of IRB decisions.

#### **f. Sharing Study Results**

Study findings will be disseminated through community forums, academic and community conference presentations, and peer-reviewed publications.

### **IV. HUMAN SUBJECTS PROTECTIONS**

#### **a. Informed Consent**

For the TLC intervention trial, written consent will be conducted in a private room, by trained TLC Program Director [name] and Program Manager [name]. Consent will occur after eligibility is determined (i.e., immediately after screening or as soon as possible thereafter) and before any research activities begin. During the COVID-19 pandemic, consent will be conducted in-person with restrictions or remotely via the e-consent module in REDCap. Both [name] and [name] have completed the web-based course, “Protecting Human Research Participants” provided by the NIH Office of Extramural Research as well as a 4-hour training session on conducting consent, protecting confidentiality and privacy, data collection, and secure storage provided by [name]. If staff feel there is a question about the need for a more formal assessment of the decisional capacity of a potential participant, they will contact the project coordinator, or study investigators, who may refer the participant to medical or psychosocial services for evaluation.

For semi-structured interviews of TLC participants and staff, we are requesting a waiver of documentation of informed consent under 45 CFR 46.117 (c). The request for waiver of documentation of consent is based on the fact that the interview data will be collected in a one-time visit, de-identified (not

linked to an individual participant name or other identifiers), and is minimal risk. This waiver is not expected to adversely impact the rights of participants because the risks of study participation are minimal and the potential for breach of confidentiality is minimal. Participants in the semi-structured interviews will receive a copy of the consent form.

Consent will be conducted immediately prior to baseline data collection (i.e., before completion of any research activities) for potential TLC intervention participants and immediately prior to the semi-structured interview for TLC participants and staff. Potential participants will be encouraged to take as much time as needed to decide whether or not to participate.

In order to avoid coercion, staff will encourage potential participants to ask questions during the consent process, assure them that their participation will not impact their relationship with staff or with the involved institutions.

Individuals who are unable to speak and understand English are excluded from this study. The primary reason for this exclusion is that the study assessments are not translated or validated for non-English speakers.

The study consent forms have been developed using the lowest reading level possible given the templated language required by the IRB of Record at Lurie Children's. The language included in the section, "What is involved in the study and how long will I be in the study?" is at the 8th grade level.

#### **b. Risks and Benefits**

Potential risks consist of being uncomfortable or emotionally upset as a result of the questions asked in the TLC intervention assessment (i.e., questions about sexual risk, substance use, mental health) or the semi-structured interviews; potential for breaches of confidentiality; risks usually associated with the collection of blood from a finger stick or from a vein in the arm, such as pain or discomfort at the site of collection, temporary bruising at that site and very rarely, the site of blood collection may become infected or need medical treatment.

In the TLC intervention study visits, it is possible that certain assessment questions regarding sexual behavior, substance use and/or mental health may make participants feel uncomfortable. However, the risk to the participant is no greater than that encountered in standard counseling relationships. Participants are free to refuse to answer any question and may terminate participation in the study at any time. All information disclosed to the research team will remain confidential if the participant chooses not to complete the study. Moreover, the participant can ask study staff to provide referrals to counselors or other means of support if they become emotionally upset. As in any study, there is always risk of inadvertent breach of confidentiality. Both Chicago House and Lurie Children's have been involved in prior studies of TW and each have considerable experience implementing measures to protect confidentiality. These measures include signed confidentiality agreements, in-service trainings on confidentiality, the assignment of study ID numbers, and the protection of study data by collecting and storing data by these ID numbers. Staff who conduct participant recruitment, screening, enrollment, and HIV/STI testing will have been trained in ethical human subject research and screening and interviewing techniques, to minimize participant risk as much as possible.

The potential risk of breach of confidentiality for semi-structured interviews will be minimized by collecting data in a de-identified format, password-protecting the audio-recording device and audio-

recordings, and destroying the audio files immediately after the audio-recordings have been transcribed and verified.

The risks associated with blood draw have been minimized by using a less invasive procedure, finger stick, when possible and by collecting a minimal amount of blood when necessary.

Individual participants may benefit by having an opportunity to receive basic services, including housing, employment, legal and medical services. Possible risks (i.e. discomfort answering questions, potential confidentiality breaches) are outweighed by the new knowledge gained from testing this intervention among the study population, a population at very high risk of HIV transmission and acquisition.

An alternative to participation in this study is referral to standard HIV/STI testing and risk reduction counseling and referral to PrEP providers.

